Study Title: The Effect of Productivity Training on Perceived Job Stress and Productivity Attitudes in Nurses: A Randomized Controlled Experimental Study

ClinicalTrials.gov Identifier: Not yet assigned

Document Type: Study Protocol

Date: 11 June 2025

Study Objectives

The primary objective of this study is to determine the effect of productivity training provided to nurses on their perceived job stress levels and productivity-related attitudes.

The specific objectives of the study are:

- To evaluate whether productivity training leads to a significant change in nurses' productivity attitudes and perceived job stress levels,
- To compare productivity attitudes and job stress levels before and after the training,
- To scientifically demonstrate the effectiveness of productivity training programs aimed at improving productivity and coping with job stress in nursing practice.

-This study aims to contribute to the limited number of experimental studies examining the relationship between job stress and productivity in nursing and to provide guidance for planning structured training programs that support nurses' professional development.

Study Design

This study is a randomized controlled experimental study with a pre-test and post-test design. Participants will be randomly assigned to experimental and control groups using a computer-generated randomization program (<http://www.randomizer.org>).

Study Setting and Period

The study will be conducted at Istanbul University Istanbul Faculty of Medicine Hospital following approval from the institutional ethics committee.

Study Population And Sample

The study population consists of nurses working at a public university hospital located in Istanbul (N = 1080).

The sample size was calculated using G*Power version 3.1.9.4. Based on a standardized effect size of 0.80 (Cohen's d) and a power of 0.95, the required sample size was determined as 70 nurses, with 35 participants in the experimental group and 35 in the control group.

Experimental Group

Participants in the experimental group will receive a structured productivity training program lasting three weeks, with a total duration of 20 hours.

The training program includes topics such as productivity concepts in nursing, time and stress management, process improvement, teamwork, leadership, use of digital tools, and coping with job stress.

The training will be delivered using various teaching methods including lectures, case analyses, simulations, practical exercises, group work, and brainstorming sessions. The program aims to enhance nurses' cognitive, affective, and practical competencies related to productivity and stress management.

Control Group

Participants in the control group will not receive any training during the study period. They will complete the same pre-test, post-test, and follow-up assessments as the experimental group.

After the completion of data collection, productivity training materials will be provided to the control group to ensure ethical fairness.

Outcome Measures

Primary Outcome Measure

Productivity Attitude Score:

Nurses' productivity attitudes will be assessed using the Productivity Attitude Scale. The total score obtained from the scale will be analyzed as the primary outcome measure.

Time Frame:

At baseline (before the training), immediately after completion of the three-week productivity training program, and three months after the training.

Secondary Outcome Measure

Perceived Job Stress Score:

Nurses' perceived job stress levels will be assessed using the Perceived Work Stress Scale (PWSS). The total score obtained from the scale will be analyzed as the secondary outcome measure.

Time Frame:

At baseline (before the training), immediately after completion of the three-week productivity training program, and three months after the training.

Data Collection Procedure

Data will be collected using the Personal Information Form, the Productivity Attitude Scale, and the Perceived Work Stress Scale. Data collection will be conducted face-to-face by the researchers after obtaining informed consent from the participants.

Ethical Considerations

Ethical approval will be obtained prior to the study. Institutional permission will be secured from the hospital administration. Participation will be voluntary, and written informed consent will be obtained from all participants. Confidentiality and anonymity will be ensured throughout the study.

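### Does naming job stress next to productivity attitudes in the primary objective unsettle which outcome is primary?

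*Protocol*

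**What the plan says.** In the protocol, Study Objectives, the main aim reads "The primary objective of this study is to determine the effect of productivity training provided to nurses on their perceived job stress levels", and the sentence carries on so that its object is the effect "on their perceived job stress levels and productivity-related attitudes". The two constructs are joined by a plain conjunction, and stress comes first. The first specific objective pairs them again: "To evaluate whether productivity training leads to a significant change in nurses' productivity attitudes and perceived job stress levels". The study title pairs them too.

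Outcome Measures ranks them. Under the primary heading, for the Productivity Attitude Scale: "The total score obtained from the scale will be analyzed as the primary outcome measure". Under the secondary heading, for the Perceived Work Stress Scale: "The total score obtained from the scale will be analyzed as the secondary outcome measure".

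Study Population And Sample gives one calculation, "Based on a standardized effect size of 0.80 (Cohen's d) and a power of 0.95", leading to 70 nurses, 35 per group. It does not say which scale the effect size refers to, and it gives neither alpha nor sidedness.

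**The concern.** Read on its own, the objective makes stress and attitudes equal partners in the primary question, while the outcome section gives stress only secondary standing. Nothing in the protocol explains the difference. In a trial with just two efficacy outcomes, three things could be at stake.

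- **Reporting.** If stress improved and attitudes did not, someone could cite the objective and say that the primary aim was met. If attitudes improved and stress did not, someone could say that it was only half met.
- **Power.** If the objective meant that both scales must show an effect, 70 nurses would give less than the stated power of 0.95.
- **Error rate.** If success on either scale were enough, with each tested at an unadjusted 5%, the chance of a false primary claim would be close to double the nominal level.

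The sample-size paragraph does not settle the matter expressly, because its effect size is attached to neither scale.

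**Working it through.** **Inputs.** From the protocol: d = 0.80, power 0.95, 35 per group. Assumed, because not stated: alpha 0.05, an independent-samples t-test, one-sided or two-sided. For the two-scale readings, also assumed: d = 0.80 on each scale.

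**Step 1: the protocol's own figure.** With 35 per group there are 68 degrees of freedom, and the noncentrality is 0.80 × √(35/2) = 3.35.

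| Test of one scale | Power at 35 per group | n per group for 0.95 |
|---|---|---|
| One-sided 0.05 | 0.952 | 35 (total 70) |
| Two-sided 0.05 | 0.910 | 42 (total 84) |

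The stated 70 is reproduced by one comparison on one outcome, tested one-sided (34 per group gives 0.947, just short). The drop from 0.952 to 0.910 comes from sidedness. It is a separate question and has nothing to do with how the objective is worded.

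**Step 2: if both scales had to succeed.** At zero correlation, joint power is the square of single-scale power:

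- one-sided: 0.9524² = 0.907
- two-sided: 0.9097² = 0.828

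At an absolute correlation of 0.5, simulation gives 0.916 and 0.847. The loss against one scale is therefore about 4 to 5 points one-sided and 6 to 8 points two-sided.

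**Step 3: if either scale sufficed, unadjusted.** With no effect on either scale and zero correlation, the false-positive rate is 1 − 0.95² = 0.0975. Simulated two-sided, it is 0.095 at an absolute correlation of 0.3 and 0.091 at 0.5.

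**Step 4: does the protocol adopt either rule?** The objective speaks of determining an effect; it sets no criterion of success. The first specific objective asks about "a significant change in nurses' productivity attitudes and perceived job stress levels", which is a question about each construct, again with no rule for combining them. The only text that assigns standing to a result is Outcome Measures. The table compares what follows from it now with what would follow if the objective were narrowed to attitudes.

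| Attitude result | Stress result | Primary claim now, under Outcome Measures | Primary claim with a narrowed objective |
|---|---|---|---|
| Positive | Positive | Supported | Supported |
| Positive | Null | Supported | Supported |
| Null | Positive | Not supported | Not supported |
| Null | Null | Not supported | Not supported |

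The last two columns agree in every row. There is one primary outcome measure before and after, so the sample stays at 70 and the figures in Steps 2 and 3 describe rules that are not in the plan.

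**The case for a change.** The strongest argument for acting is that the contradiction lies wholly inside this protocol, so an analysis plan not shown could not remove it. A testing order set there would still leave a primary objective that names two outcomes. The word primary is attached to stress in one section and withheld in another. The repair would be a sentence or two, and on the face of the document there is time: ethical approval is still to be obtained and no registry identifier has been assigned.

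Part of this stands. The objective is loosely worded, narrowing it would cost nothing, and a sponsor revising the document for other reasons could tidy it.

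What does not stand is that the wording leaves the primary outcome open. An objective states the question in general terms; the outcome section says which measurement answers it, and here it does so under two separate headings. A stress result presented as the primary finding would conflict with the protocol's own label, and any reader could see that. The risk concerns reporting; it does not bias the primary analysis.

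The unattached effect size, "standardized effect size of 0.80", is missing detail about the sample-size justification. It does not show that stress was meant to be primary. If anything, a figure that one outcome reproduces sits better with the stated hierarchy than with two primary outcomes, although that is an inference from the assumed one-sided test.

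**Conclusion.** The mismatch between the objectives and the outcome hierarchy is genuine, but it is one of wording and calls for no change to the plan. Outcome Measures fixes the attitude total as the sole primary outcome and the stress total as secondary, clearly enough that an analyst would proceed the same way with or without an edit. The effect of alignment on sample size, power, error rate and primary claim is nil.

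The joint power of 0.907 (one-sided) or 0.828 (two-sided) and the 9-10% false-positive rate are arithmetically correct under their assumptions: alpha 0.05, d = 0.80 on each scale for the power figures, and the correlations shown. They measure success rules that the protocol does not state, so they are not costs of the trial as planned. The conclusion rests on reading the outcome section as the text that governs the primary claim. It would change only if the sponsor intended both scales to be primary, and nothing in the outcome section or the single sample-size calculation suggests that.

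### The 70 nurses at power 0.95 are calculated as independent observations, although only the trained arm shares a course with group work; if nurses taught together have correlated scores, power is lower, by an amount the protocol does not let anyone fix

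*Protocol*

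**What the plan says.** Under Study Design, nurses are randomised individually: "Participants will be randomly assigned to experimental and control groups using a computer-generated randomization program". Under Study Population And Sample, the calculation was done in G*Power: "Based on a standardized effect size of 0.80 (Cohen's d) and a power of 0.95", and "the required sample size was determined as 70 nurses, with 35 participants in the experimental group and 35 in the control group". That passage gives no alpha, sidedness, test, ICC or design effect.

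Under Experimental Group, the trained arm receives a "structured productivity training program lasting three weeks, with a total duration of 20 hours", and the teaching methods are "lectures, case analyses, simulations, practical exercises, group work, and brainstorming sessions". Under Control Group, "Participants in the control group will not receive any training during the study period".

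The protocol does not say whether the 35 trained nurses form one class or several, how large the classes are, or how many trainers there are. It states no analysis model.

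**The concern.** Individual randomisation with joint teaching in one arm only is a partially nested design. Nurses who spend 20 hours together in group work share a trainer, a class atmosphere and each other's views. The primary outcome is an attitude score, so some similarity within a class after training is plausible. Any such similarity makes the mean of the trained arm more variable than 35 independent nurses would, while the control mean is unaffected by it. A calculation that treats all 70 nurses as independent then overstates power.

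The class structure is also a delivery decision, taken when the course is given. If class and trainer are not noted then, a later analysis cannot model them. If all 35 nurses form one class, the trial contains no information on how results would differ with another class or trainer, and enlarging that class would not supply it.

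**Working it through.** **Inputs.** From Study Population And Sample: d = 0.80, power 0.95, 35 per arm. Not in the protocol, so assumed: alpha 0.05; independent two-sample t test, tried one-sided and two-sided; total SD 1 in both arms; no dropout; k classes of m = 35/k nurses; correlation ICC within classes, in the trained arm only. The main range is ICC 0.02 to 0.05, with 0.01 and 0.10 as outer values.

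**Step 1: reproduce 70.** Noncentrality = 0.80/√(2/35) = 3.347, with 68 df.
- One-sided (critical value 1.668): power 0.952, and 35 per arm is the smallest size reaching 0.95. This reproduces the plan.
- Two-sided (critical value 1.995): power 0.910. Reaching 0.95 would take 42 per arm, 84 in all.

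So 70 is the unclustered result, with no margin for anything else.

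**Step 2: add correlation in the trained arm.** Design effect DE = 1 + (m − 1) × ICC; SE² = (1 + DE)/35; noncentrality = 0.80/SE.

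Example, three classes (m = 11.67), ICC 0.05: DE = 1 + 10.67 × 0.05 = 1.533; SE = √(2.533/35) = 0.269; noncentrality 2.974; one-sided power with 68 df 0.903.

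**Step 3: count the few classes in the degrees of freedom** (Satterthwaite): df = (DE + 1)²/(DE²/(k − 1) + 1/34). Same example: 2.533²/(1.533²/2 + 1/34) = 5.3, and one-sided power falls to 0.82.

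| Classes | ICC | DE | One-sided, 68 df | Two-sided, 68 df | One-sided, small-sample df | Two-sided, small-sample df |
|---|---|---|---|---|---|---|
| none | 0 | 1.00 | 0.95 | 0.91 | – | – |
| 5 | 0.02 | 1.12 | 0.94 | 0.89 | 0.92 | 0.85 |
| 5 | 0.05 | 1.30 | 0.93 | 0.87 | 0.90 | 0.82 |
| 3 | 0.02 | 1.21 | 0.93 | 0.88 | 0.88 | 0.77 |
| 3 | 0.05 | 1.53 | 0.90 | 0.83 | 0.82 | 0.68 |
| 1 | 0.02 | 1.68 | 0.89 | 0.81 | not estimable | not estimable |
| 1 | 0.05 | 2.70 | 0.79 | 0.68 | not estimable | not estimable |

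The 68-df columns are optimistic, because they treat the inflated standard error as if 68 df were available to estimate it. The single-class rows are arithmetic only: no data from the trial could estimate that standard error.

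**Step 4: separate sidedness from clustering.** With three classes, ICC 0.02 and 68 df, two-sided power is 0.880. Of the drop from 0.952, 0.042 comes from testing two-sided (0.952 to 0.910) and 0.030 from clustering (0.910 to 0.880).

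**Step 5: the ends of the range, one-sided, 68 df.** Classes of 5 to 7 with ICC 0.01 to 0.02 give 0.949 to 0.942, a loss of at most about one point. At ICC 0.10, three classes give 0.85 and one class 0.64.

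**Step 6: if an analysis treated nurses as independent.** The true standard error would be √((1 + DE)/2) times the reported one. For ICC 0.02 to 0.05 this is 1.05 to 1.13 times with three classes and 1.16 to 1.36 times with one class.

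**The case against.** **Class structure is inferred.** The teaching methods point to joint teaching, but the protocol sets out no timetable, class size or trainer number, and gives no ICC. A reader might infer that trained nurses' scores are bound to be correlated and that 0.95 is therefore plainly wrong. The document does not support that: the shortfall needs a positive ICC, and a material one needs larger classes or a non-trivial ICC. This part of the objection stands.

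**The analysis is not shown.** A reader might also infer that the trial's false-positive rate exceeds 5% or that its confidence intervals will be too narrow. That would criticise an unadjusted comparison that the protocol never specifies. The analysis model may properly sit in a SAP, so this stands only as a conditional warning.

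**Silence on recording is not evidence of non-recording.** The forms named under Data Collection Procedure do not mention class or trainer, but this does not show that membership will go unrecorded. Even without individual membership, a sensitivity analysis over assumed ICCs could be run from class sizes alone.

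**Baseline adjustment could offset the loss.** The attitude score is also measured before training. With an assumed correlation of 0.5, the variance is multiplied by 1 − 0.5² = 0.75. Three classes at ICC 0.05 then give about 0.96 one-sided and 0.92 two-sided on the 68-df type of calculation. This is a fair point: the net shortfall is not established. But the stated calculation claims no such gain. The same arithmetic with 5.3 df gives about 0.91 and 0.79.

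What survives is that the power statement is in the protocol and rests on independence, and that the class structure has to be settled when the course is organised.

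**Conclusion.** The point holds conditionally. The 35 + 35 is an independent-observations result with no allowance for clustering, while the design gives only one arm a shared course. Any positive correlation among nurses taught together puts true power below the calculated figure.

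The size rests on assumed class numbers and ICCs. On the one-sided basis that reproduces 70, it runs from about one point (classes of 5 to 7, ICC 0.01 to 0.02) to about 16 points (one class, ICC 0.05: 0.95 to 0.79), before any small-sample penalty.

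It would be tempting to set the two-sided clustered figures directly against 0.95 and blame clustering for the whole gap. That is not supported: about four points of the gap come from sidedness, which the protocol leaves unstated. Nor would it be sound to adopt 0.83 to 0.88 as the three-class two-sided power, because those figures use 68 df. An analysis with small-sample degrees of freedom gives about 0.68 to 0.77.

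**What to change.** Before training starts:

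1. Fix the number of classes and trainers for the 35 nurses, and record each nurse's class and trainer in the data set.
2. State alpha and sidedness, and restate power as a range over assumed ICCs. Calculate it with the same degrees of freedom as the planned analysis, and show the sidedness effect and the clustering effect separately.
3. If all 35 are taught as one class, state that class and trainer variation cannot be estimated, and limit the conclusion to the course as delivered.

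The choice of analysis model can be left to the SAP. If that analysis compares nurses as independent while scores are correlated within classes, the standard error of the training effect would be too small.

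The cost is a less favourable power figure and one extra variable for class and trainer. These changes require no extra nurses or sessions. If the analysis does account for few classes, confidence intervals will be noticeably wider, as the small-sample columns imply.
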